2. LIST OF ABBREVIATIONS

Term	Definition / description
ADR	Adverse Drug Reaction
AE	Adverse Event
AF	Atrial Fibrillation
ATC	Anatomical Therapeutic Chemical
BI	Boehringer Ingelheim
CHA ₂ DS ₂ -VASc score	Congestive heart failure, Hypertension, Age (≥ 75), Diabetes mellitus, Stroke/TIA, Vascular disease, Age 65-74, Sex category
ECG	Electrocardiogram
eCRF	Electronic Case Report Form
EoT	End-Of-Text
HAS-BLED	Hypertension, Abnormal renal and liver function, Stroke (1 point), Bleeding history or predisposition, Labile INR, Elderly (>65 years), Drugs and Alcohol.
IC	Informed Consent
ICH	International Conference on Harmonisation
INR	International Normalized Ratio
IPV	Important Protocol Violation
ISPE	International Society for Pharmaceutical Engineering
MedDRA	Medical Dictionary for Regulatory Activities
MQRM	Medical Quality Review Meeting
NVAF	Non-Valvular Atrial Fibrillation
PACT-Q [®]	Perception of Anticoagulant Treatment Questionnaire
SD	Standard Deviation
SEAP	Statistical and Epidemiological Analysis Plan
SEASK	South East Asia South Korea
VKA	Vitamin K Antagonist
WHO	World Health Organization

3. INTRODUCTION

As per ICH E9 (1) and the ISPE Guidelines of Good Pharmacoepidemiology Practice (2), the purpose of this document is to provide a more technical and detailed elaboration of the principal features of the analysis described in the protocol, and to include detailed procedures for executing the statistical analysis of the data. This document describes the final analysis at the end of trial as well as the preliminary assessment which will be performed for Cohort B when approximately half of the target sample size is reached.

This SEAP assumes familiarity with the registry protocol, including Protocol Amendments (if present). In particular, the SEAP is based on the planned analysis specification as written in the registry protocol Section 9 “Research Methods”. Therefore, SEAP readers may consult the registry protocol for more background information on the study, e.g., on study objectives, study design and population, treatments, definition of measurements and variables, planning of sample size.

SAS® Version 9.3 or higher will be used for all analyses.

4. CHANGES IN THE PLANNED ANALYSIS OF THE STUDY

4.1 SUMMARY OF CHANGES TO THE STUDY

Patient analysis set has been updated to include all patients who took the prescribed treatment and without an important protocol violation.

For Cohort B, no formal interim analysis will be performed; instead a preliminary analysis will be performed to assess the comparability of the matched Pradaxa[®] and VKA patients based on propensity scores matching analysis when approximately half of the target sample size is reached.

5. OUTCOMES

This non-interventional study is designed to describe the non-valvular atrial fibrillation patient's treatment perception by using the PACT-Q at three time-points (at baseline, during initiation period and during the continuation period) (objective 1) and to characterize the patient population (incl. dosing) in the participating SEASK countries (objective 2).

The data will be collected for two cohorts of patients:

Cohort A: Patients having been treated with VKA and now being switched to Pradaxa[®]

Cohort B: Patients newly diagnosed with non-valvular atrial fibrillation and initiated on either Pradaxa[®] or VKA.

5.1 MAIN OUTCOMES

For objective 1, the main variables of interest are mean PACT-Q2 scores at second and last assessment compared to baseline assessment for Cohort A (switcher), and mean PACT-Q2 scores at second and last assessment between treatment groups for Cohort B (newly initiated).

For objective 2, the main variables of interest are patient baseline characteristics and demographics, including age, gender, CHA₂DS₂-VASc score, HAS-BLED score (modified HAS-BLED for newly initiated patients), kidney function (creatinine clearance), stroke and/or bleeding related risk factors in medical history and at baseline, co-morbidities, concomitant therapies, dosing of Pradaxa[®], as well as duration of previous VKA treatment (for Cohort A).

5.2 SECONDARY OUTCOMES

The secondary outcomes to be analysed are mean PACT-Q2 score at last assessment compared to second assessment for Cohort A (switcher), and description of PACT-Q1 items at baseline for Cohort B (newly initiated).

6. GENERAL ANALYSIS DEFINITIONS

6.1 EXPOSURE

This is a non-interventional multi-national, multi-centre study based on newly collected data. Patients will either be switched from vitamin K antagonist (VKA) treatment to Pradaxa[®] (Cohort A) or newly initiated on Pradaxa[®] or VKA (Cohort B).

- Pradaxa[®] 110 mg hard capsules
- Pradaxa[®] 150 mg hard capsules
- Vitamin K antagonist

Patients will receive daily dose of Pradaxa[®] (hard capsules contain Dabigatran etexilate) according to the Summary of Product characteristics and physician's discretion. The choice of VKA and the appropriate dosing is in the discretion of the physician.

Patients will be followed over an observation period of 6 months. Data will be collected at three time points:

1. At Baseline (initiation on Pradaxa[®] or VKA)
2. 30-45 days after initiation on Pradaxa[®] or VKA (initiation period)
3. 150-210 days after initiation on Pradaxa[®] or VKA (continuation period)

The visit windows above for Visit 2 and Visit 3 should be seen as guidance for the treating physician. Visit schedule deviations are expected as the visits are being scheduled according to local clinical routine. For analysis purpose, Visit 2 data that were collected between 7 and 124 days after initiation will be included (rationale for the lower limit is that steady state on Pradaxa is achieved after 3 days, and first side effects also might occur after a 1st or 2nd intake; rationale for the higher limit is to make sure that there is no overlap with Visit 3). Visit 3 data that were collected between 125 and 365 days after initiation will be included for analysis.

6.2 IMPORTANT PROTOCOL VIOLATIONS

Patients with important protocol violations (IPVs) will be documented. The following list of IPVs will be used. Additional IPVs may be defined during the course of the study. Those will be assessed during the Medical and Quality Review meetings (MQRM); if the list of IPVs needs to be enlarged, it will be documented in the report planning meeting minutes before database lock.

Table 6.2: 1 Important protocol violations

Category / Code	Description	Requirements	Excluded from
A	Entrance criteria not met		
A1	Inclusion criteria not met		
A1.1	Informed consent not given	Date of written informed consent missing	All
A1.2	Informed consent given too late	Date of written informed consent after date of baseline visit, date of first dose taken, or PACT-Q date	All

Table 6.2: 1 (continued) Important protocol violations

Category / Code	Description	Requirements	Excluded from
A1.3	Age < 18 years		All
A1.4	No diagnosis of non-valvular atrial fibrillation (NVAF)	For Cohort A, no existing diagnosis of NVAF, or for Cohort B, no new diagnosis of NVAF	All
A1.5	< 3 months of continuous VKA treatment for stroke prevention prior to baseline assessment	For Cohort A only, less than 3 months of continuous VKA treatment for stroke prevention prior to baseline assessment	All
A1.6	Previous treatment for stroke prevention	For Cohort B only, patients had previous treatment (i.e. used an oral anticoagulant within 1 year prior to enrolment) for stroke prevention	All
A1.7	IC prior to site initiation visit	Date of written informed consent prior to site initiation	All
A2	Exclusion criteria violated		
A2.1	Contraindication to the use of Pradaxa® or VKA		All
A2.2	Pradaxa® or VKA used for any other conditions	Patients receiving Pradaxa® or VKA for any other condition than stroke prevention in atrial fibrillation	All
A2.3	Participating in other clinical trial	Current participation in any clinical trial of a drug or device	All
A2.4	Participating in a Registry on the use of oral anticoagulation in AF	Current participation in a Registry, e.g. the Gloria registry program, on the use of oral anticoagulation in AF	All
Z	Other		
Z1	Patients on Pradaxa with CrCl < 30 ml/min		All

6.3 PATIENT SETS ANALYSED

The main analysis population will consist of all eligible patients [i.e. all patients who took the prescribed treatment and without an important protocol violation (see [Table 6.2: 1](#))] from all participating countries.

6.5 POOLING OF CENTRES

Centre will not be used as a factor in any analysis model; therefore this topic is not applicable.

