9.2 SETTING

It is planned that data of approximately 1790 patients will be collected from approximately 80 sites in 6 SEASK countries. Planned participating countries are Indonesia, Malaysia, Singapore, South Korea, Thailand and Vietnam.

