9.5 STUDY SIZE

It is planned that a total of approximately 1790 patients from 6 SEASK countries will be recruited for Cohort A and Cohort B.

Baseline demographics and disease characteristics of the patient population will be described by estimates and confidence intervals (CIs) overall (for Cohort A), by anticoagulation treatment (for Cohort B), and by additional relevant categories as specified in Section 9.7.2 and the SEAP. Categorical attributes will be estimated with the precision (i.e. width of descriptive 95% confidence interval) described in Table 9.5: 1, according to sample size and prevalence of the attribute.

Table 9.5: 1 Width of 95% confidence interval by sample size and prevalence of attribute

Prevalence of attribute		Sample size (overall or per subgroup)			
		200	500	1000	2000
10%	Expected n	20	50	100	200
	95% CI width	8.80	5.46	3.82	2.68
20%	Expected n	40	100	200	400
	95% CI width	11.53	7.20	5.05	3.55
30%	Expected n	60	150	300	600
	95% CI width	13.13	8.21	5.77	4.06
40%	Expected n	80	200	400	800
	95% CI width	13.99	8.77	6.17	4.34
50%	Expected n	100	250	500	1000
	95% CI width	14.26	8.94	6.29	4.43

* Calculations are based on the Clopper-Pearson method.

For example, for a population attribute with a prevalence of 20%, a total sample size of 1000 patients for Cohort A allows this proportion to be estimated with a precision of 5.05% (i.e. width of 95% CI).

The planned total sample size of 1790 patients is jointly determined by the following sample size assessments and additional non-statistical considerations, including feasibility assessments for the participating countries.

Due to the limited number of publications on PACT-Q2 ([R15-1314](#), [R15-1316](#), [R15-1359](#)) and the lack of information regarding the clinical meaning of changes in PACT-Q2 scores, sample size assessments are performed using standardized mean differences. In the context of this study, they represent the mean differences in PACT-Q2 scores between two assessments (for Cohort A) or between the Pradaxa® and VKA groups (for Cohort B) divided by the corresponding standard deviations. In general, a standardized effect size of 0.2 is considered a small change, 0.5 a moderate change, and 0.8 a large change.

For Cohort A, assuming a 2-sided alpha of 0.05 and a 20% loss to follow-up, a total sample size of 598 patients will provide over 80% power to detect a standardized mean difference of 0.13 in PACT-Q2 scores between two assessments.

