9.9 LIMITATIONS OF THE RESEARCH METHODS

Consecutive enrolment will be employed to ensure that specific types of patients are not selected by site staff to participate.

VKA has been the mainstay of SPAF for many years. It is widely available, affordable but does require regular INR monitoring. Pradaxa[®] is more expensive, may or may not be reimbursed but doesn't require the continual INR monitoring. There are a number of different types of bias that could influence the data collection and analysis from these cohorts such as selection bias, information bias and channelling bias.

The study is designed to collect new data. The entry criteria are non-restrictive which will permit the enrolment of a broad patient population. The choice of treatment is at the discretion of the investigator. Therefore the data collected in this study should reflect the real world treatment patterns and patient characteristics.

Selection bias:

Selection bias could occur at both the site (physician) level and the patient level. If sites where Pradaxa[®] is used frequently differ systematically with respect to patient or the routine procedures from sites that use Pradaxa[®] less frequently, the between site difference could lead to non-comparability between the patients. To minimize the site level selection bias, the goal is to have participating centres that have access to all available treatment options for SPAF that are approved for use in that country.

Selection bias at the patient level could occur if sites preferentially enrol specific patients into the study. To minimize selection bias at the patient level, consecutive enrolment is performed.

- **Information / observer bias:**

Information or observer bias may occur when information is collected differently between

two groups. E.g. if the observer/physician has more knowledge about the use of VKA treatment, the patients exposure to VKA treatment or the disease status and development as compared to Pradaxa[®]. Also, a VKA patient will be more often seen. Such information may result in differences in the way information is collected, measured or interpreted by the investigator in each of the treatment groups (cohort A or B (B1, B2)). The use of a standardized protocol and eCRF for data collection, but also the use of standardized questionnaires (PACT-Q) which have to be completed by the patients themselves, will minimize the information/observer bias.

- **Loss to follow-up:**

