7.6 MAIN ANALYSES

Due to the nature of this non-interventional study, there is no (confirmatory) hypothesis testing foreseen in a strict statistical sense. Analyses are descriptive in nature and confidence intervals and p-values from statistical models are used for exploratory purposes.

For the PACT-Q1, no global score is calculated as each item is analysed individually (3).

Within the PACT-Q2, items for convenience and for burden of disease and treatment are reversed (reversed score = 6 – item score), added together and rescaled on a 0-100 scale to obtain the convenience dimension score. Items for anticoagulant treatment satisfaction are summed and rescaled on a 0-100 scale to determine the satisfaction dimension score (3).

The convenience and satisfaction scores are calculated separately only if at least 50% of items of the dimension for a patient at a visit are completed. For convenience and satisfaction dimension scores, if at least 50% of items are completed (non-missing) for a dimension, the missing items of a patient at a visit are replaced by the mean of non-missing items of the dimension obtained at the same visit for the same patient. Then sums of items of dimensions are calculated and rescaled on a 0-100 scale as follow (3):

$$\text{Score} = 100 \times (\text{sum} - \text{minimal possible sum}) / (\text{highest possible sum} - \text{minimal possible sum})$$

The PACT-Q1 scores which were collected after first dose, the PACT-Q2 scores which were collected more than 1 day after patients discontinued from the treatment, and the PACT-Q scores which were collected using incorrect PACT-Q procedure will be excluded from the summaries or analyses.

For Cohort A, the mean convenience and satisfaction dimension scores of PACT-Q2 at the second assessment (Visit 2) and last assessment (Visit 3) will be compared with the baseline assessment (Visit 1) using paired t-tests.

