 - Variable selection will be performed with caution to avoid the inclusion of highly correlated variables as well as over-parameterization.
 - All covariates from the list above will be set as required covariates in the propensity score model to ensure balance of baseline characteristics of patients. If any additional covariates are deemed necessary to be included in the propensity score model, they need to be defined before database lock.

Pradaxa[®] and VKA patients will then be matched based on propensity scores using a variable ratio, parallel, balanced 1:n, nearest neighbour matching algorithm with a caliper width of 0.05 and without replacement. The publicly available SAS macro provided by Rassen et al. (5) will be used.

Finally, the percentage of Pradaxa[®] and VKA patients that are matched with an appropriate maximum ratio (e.g. 2:1) according to the actual patient distribution will be calculated to assess the comparability of the two patient populations, and to estimate the loss of patients from the comparative analysis.

For the final comparative analysis for Cohort B, Pradaxa[®] and VKA patients will be matched based on propensity scores following the same approach as described above. To assess the performance of the propensity score matching procedure, patient demographics and disease characteristics at baseline will be descriptively summarized again for the matched patients by treatment. For each matched set that includes multiple Pradaxa patients, the mean PACT-Q2 score will be calculated for the Pradaxa patients and used in the final comparative analysis. Finally, the mean PACT-Q2 scores at each of the second and last assessments will be compared between the matched Pradaxa[®] and VKA patients using paired t-tests.

For both cohorts, the primary analyses will be based on the actual anticoagulation treatment the patients receive (i.e. “as treated” analysis). A patient is considered to have permanently discontinued initial anticoagulation treatment if other relevant anticoagulation treatment is initiated or otherwise dependent on the duration of treatment interruption. Whether a patient discontinued from the Pradaxa[®] or VKA is recorded on the eCRF. Patients who have permanently discontinued initial anticoagulation treatment at the time of an assessment will be excluded from all analyses where data from that assessment is included.

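### The PACT-Q2 paired t-tests make no allowance for correlation within about 80 sites, so the nominal 95% coverage of their intervals is not assured

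*SAP*

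**What the plan says.** Protocol 9.2 expects that "data of approximately 1790 patients will be collected from approximately 80 sites in 6 SEASK countries". SAP 6.5 says that "Centre will not be used as a factor in any analysis model" and on that ground treats pooling of centres as not applicable.

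The main analyses are in SAP 7.6. In Cohort A, the convenience and satisfaction scores at Visits 2 and 3 "will be compared with the baseline assessment (Visit 1) using paired t-tests". In Cohort B, mean scores at each of the two follow-up assessments "will be compared between the matched Pradaxa[®] and VKA patients using paired t-tests". Where a matched set holds several Pradaxa patients, their scores are first averaged.

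Neither document plans a cluster-robust standard error, a random site effect or a sensitivity analysis by site, and Protocol 9.5 includes no design effect in the sample size. The Cohort B propensity model in SAP 7.6 contains pooled country (South Korea or not), type of physician, type of hospital or practice, and practice owner, but not site. Protocol 9.7.2 promises 95% confidence intervals. Protocol 9.7.1 and SAP 7.6 call the intervals and p-values exploratory.

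**The concern.** A paired t-test removes the dependence inside a pair. It still assumes that the pairs are independent of each other: patients' change scores in Cohort A, matched-set differences in Cohort B. Leaving centre out of the model does not make that assumption true, so the reason given in SAP 6.5 does not settle the matter.

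Site correlation is plausible here. Protocol 9.9 warns, under selection bias, that if sites differ systematically in patients or routine procedures, "the between site difference could lead to non-comparability between the patients". Several PACT-Q2 items (B7, B8, D5) ask about appointments, medical follow-up and how follow-up is organised, which the site largely determines. Protocol 9.9 also notes that Pradaxa does not need continual INR monitoring. How much relief a switch brings may therefore depend on how a site ran that monitoring.

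At stake are the width of the confidence intervals and the reading of the descriptive p-values. The effects that the study is sized for are small (0.13 and 0.14 standard deviations), so a modest error in the standard error can change how a result looks.

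**Working it through.** **Inputs from the documents.** About 80 sites (Protocol 9.2). Cohort A: "a total sample size of 598 patients will provide over 80% power to detect a standardized mean difference of 0.13", at two-sided alpha 0.05 and after losing 20% of patients (Protocol 9.5). Cohort B: 1192 patients, 1:1, 30% loss to follow-up and matching, difference 0.14, over 80% power (Protocol 9.5). **Assumed, because the documents give no value:** the ICC, equal site sizes, and that all 80 sites contribute to each cohort.

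**Step 1: the plan's own power, under independence.** Power = Φ(d√n − 1.96).
- Cohort A: n = 598 × 0.8 = 478. 0.13 × √478 − 1.96 = 0.882, so power is 81.1%.
- Cohort B: n = 1192 × 0.7 / 2 = 417 pairs. 0.14 × √417 − 1.96 = 0.899, so power is 81.6%, with 0.14 read as the mean difference over the SD of the pair differences.

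Both agree with the stated figure of over 80%. The sample size therefore rests on independence between pairs.

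**Step 2: Cohort A with site correlation.** A site effect that is the same at every visit cancels in the within-patient change. The relevant ICC is therefore that of the change score, not that of the score level. With m = 478/80 = 5.975 patients per site:
- design effect D = 1 + (m − 1) × ICC
- true SE = reported SE × √D
- actual two-sided error = 2 × [1 − Φ(1.96/√D)]
- power with a correct SE = Φ(0.13 × √(478/D) − 1.96)

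| ICC of change | D | √D | Actual error | Power, correct SE |
|---|---|---|---|---|
| 0 | 1.00 | 1.00 | 5.0% | 81.1% |
| 0.01 | 1.05 | 1.02 | 5.6% | 79.2% |
| 0.05 | 1.25 | 1.12 | 7.9% | 72.0% |
| 0.10 | 1.50 | 1.22 | 10.9% | 64.2% |

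Uneven site sizes make this worse. With coefficient of variation 1, D = 1 + (2m − 1) × ICC, and the error is 11.5% at ICC 0.05 and 17.6% at ICC 0.10.

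**Step 3: Cohort B with site correlation.** Cohort B has no baseline PACT-Q2, so here the ICC of the score level matters. The null case was simulated with 4000 runs per cell, 80 sites of 10 patients (800, close to 2 × 417 = 834), and 1:1 pairs formed at random across sites. Actual two-sided error:

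| Spread of drugs over sites | ICC 0.05 | ICC 0.10 | ICC 0.20 |
|---|---|---|---|
| 1:1 inside every site | 5.0% | 3.8% | 2.8% |
| Pradaxa share moderately variable, Beta(5,5) | 5.5% | 5.9% | 6.7% |
| Strongly variable, Beta(1,1) | 6.2% | 8.6% | 11.6% |
| One drug only per site | 10.9% | 14.9% | 24.3% |

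The Monte Carlo standard error at 5% is √(0.05 × 0.95 / 4000) = 0.34 percentage points. The two extreme rows can be checked by formula. With 1:1 inside every site, site effects cancel between arms although the pairs ignore site, and D = 1 − ICC. At ICC 0.20, √0.80 = 0.894 and the error is 2.8%. With one drug per site, D = 1 + 9 × ICC. At ICC 0.20, √2.8 = 1.673 and the error is 24.2%. Both agree with the simulation.

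The simulation does not reproduce the SAP's matching on the propensity score or its variable-ratio sets. It shows direction and rough size only.

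**The case against.** **No ICC is given, and it could be zero.** This stands. At ICC 0 the Cohort A error is exactly 5.0%, and at 0.01 it is 5.6%. A reader might infer that the standard errors and p-values are wrong as planned. The documents do not support that; they show only that correct coverage rests on an untested assumption.

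**The site differences that Protocol 9.9 describes concern selection and comparability.** This also stands in part. Stable differences between sites cancel in the Cohort A change scores. Only site variation in the change matters, and an ICC of 0.05 to 0.10 for that is an assumption.

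**In Cohort B the direction is open and the extreme scenarios are unlikely.** Largely right. Protocol 9.2.1 selects sites that regularly prescribe both treatments and lets the sponsor close a sub-cohort against country or site targets, and the propensity score takes up part of the site difference. With moderate drug mix the error stays near nominal (5.5% to 6.7%). A reader might infer that ignoring site always makes intervals too narrow; the balanced case shows the opposite. However, the 1:1 control in Protocol 9.2.1 guarantees no even split within each site. An unknown direction is a reason to estimate the standard error in a way that fits the data.

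**SAP 6.5 does not forbid a remedy.** Correct. It excludes centre as a model factor and leaves a robust standard error possible, but none is planned.

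**Everything is exploratory.** This limits the weight of the point, since no confirmatory error rate is at risk. It does not remove the point: an interval labelled 95% should have about that coverage in a descriptive study too.

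**Conclusion.** The planned analysis makes no allowance for site clustering, so nominal coverage of the PACT-Q2 intervals is not assured. That is as far as the documents go.

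In Cohort A, any positive ICC of the change score makes the reported standard error too small: by a factor of 1.02 to 1.22 for an ICC of 0.01 to 0.10, with an actual error of 5.6% to 10.9%. This assumes about 6 patients at each of 80 equal sites. In Cohort B the simulated error runs from 2.8% to 24.3% over an ICC of 0.05 to 0.20. The upper end needs sites that use one drug only, which the site selection makes unlikely, and even the direction is not fixed.

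This is a cheap improvement to an exploratory analysis, not a demonstrated error in it.

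**What to change.** In SAP 7.6, keep the point estimates and change how their uncertainty is calculated.

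- **Cohort A:** report the mean change with a site-cluster-robust standard error and 95% confidence interval.
- **Cohort B:** fit a patient-level weighted regression of the score on treatment in the matched sample. Give each VKA patient weight 1 and each Pradaxa patient weight 1/n, where n is the number of Pradaxa patients in the set with a score at that visit. Use only sets with scores on both sides. The treatment coefficient is then the mean over sets of (Pradaxa mean − VKA score), which is the planned estimate. Cluster the standard errors on both matched set and site: variance by set, plus variance by site, minus variance by the set-by-site combination. A random site intercept, or clustering on site alone, is not defined for the set differences, because a set can span several sites.
- **Reporting:** give the site ICC of the change score in Cohort A and of the score at each visit in Cohort B.
- **SAP 6.5:** replace the not-applicable statement with a reference to this method.

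No new data are needed. The cost is a little more programming, a short SAP amendment, and intervals that may be somewhat wider. The results stay exploratory.
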